**Table 4: Clinical Laboratory Potentially Clinically Significant Criteria**

Parameter	Threshold (Low Criterion/ High Criterion)	Low Criterion (Subcategories)	High Criterion (Subcategories)
Iron Parameter (unit)			
Ferritin (ng/mL)	Clinical	NA	High 1: > 500 to 1000, High 2: > 1000
Transferrin saturation (%)	Clinical	NA	High 1: > =50 to <70 High 2: > =70
Hematology			
Hemoglobin (g/dL)	CTCAE grade 3 /Clinical	< 8.0	> 13
Chemistry			
Phosphorous (mg/dL)	CTCAE grade 2 /Clinical	Low 1: ≥2.0 to <2.5, Low 2: < 2.0	> 9.0
Liver Function			
Hy's Law (Impaired Liver Function)	CTCAE grade 2 /DILI*	NA	High 1: ALT or AST > 3 x ULN to 5 x ULN High 2: ALT or AST > 5 x ULN
Total serum bilirubin value	DILI*	NA	> 2xULN

\*DILI = Drug Induced Liver Injury

## 9.5. Vital Signs

No tables of descriptive statistics or by subject listings for the vital signs, i.e., seated systolic and diastolic blood pressures (mmHg), heart rate (bpm) and weight, values and change from baseline will be presented.

Each value's classification of low, normal or high based on the parameter's central laboratory reference range and the following clinical significance and CTCAE classifications will be included in an ADaM dataset:

---

Document: \\quintiles.net\enterprise\apps\sasdata\sasb\sas\Keryx\KRX-0502\Biostatistics\Documentation\SAP\

Author: [REDACTED]

Version Number:

1.1

- Diastolic Blood Pressure < 50 mmHg, Systolic Blood Pressure < 80 mmHg (based on clinical significance),
- Diastolic Blood Pressure  $\geq$ 100 mmHg, Systolic Blood Pressure  $\geq$ 160 mmHg (based on CTCAE grade 3)
- Pulse < 55 beats/min, Pulse >110 beats/min (based on clinical significance).

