6.1.3. Safety Endpoints

Safety evaluations will be based on the following:

- Incidence, seriousness, intensity, duration, and type of AEs
- Clinically significant changes in the subject's vital signs and laboratory test results.

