15. STATISTICAL METHODS AND PLANNED ANALYSES

15.1. General Considerations

All statistical analyses will be performed using Version 9.4 or later of Statistical Analysis Software (SAS®).

Data summaries will use descriptive statistics (number of subjects [n], mean, standard deviation [SD], median, minimum, and maximum) for continuous variables and frequency and percentage for categorical and ordinal variables. If there are missing values, the number missing will be presented but without a percentage. All data collected will be included in by-subject data listings.

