15.8.1. Vital Signs

Vital signs (seated heart rate and blood pressure after at least 5 minutes of rest) will be summarized as changes from Baseline and will be classified as low, normal, or high based on reference ranges pre-specified in the SAP. Vital sign abnormalities will be summarized using shift tables for all subjects and by randomized dose group.

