### **3.2.3. Safety Endpoints**

Safety evaluations are based on the following:

- Incidence, seriousness, intensity, duration, and type of AEs
- Clinically significant changes in laboratory test results and vital signs

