## 9. SAFETY AND TOLERABILITY

Safety and tolerability evaluation will be included in the 24-Week Analysis and the Final Analysis.

The safety data includes adverse events, vital signs and clinical laboratory measurements.

Adverse events that begin after the first administration of study medication or pre-existing conditions that worsen after the first dose of study medication are considered TEAEs. If, based upon the data recorded in the eCRF and/or the procedure for imputing the start date given in section 9.2.2, it is not possible to classify an AE as treatment emergent or not, then classify the AE as a TEAE.

For the 24-Week Analysis, since any table, listing or figure produced will only include statistics based upon the Screening period and Dose Titration treatment period:

- No adverse event that starts or worsens after the Week 24 visit date will be included in summaries of TEAEs and
- In calculating the subject months of study drug exposure only those days of treatment prior to the Week 24 visit will be counted since subjects are to delay taking their study drug on the day of planned site visits until after the site visit.

For the Final Analysis, all observations up to and including those for the Week 48 visit date will be included in identifying TEAEs and calculating subject months of study drug exposure.

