## 9.6. Summary of Changes from Protocol-Specified Analyses

- The protocol states that “All subjects who are randomized and take at least 1 dose of study medication will be included in the Safety Analysis Set.” However, the Safety Analysis Set is being defined as the set of all subjects who receive at least one dose of study medication, to allow for the highly unlikely possibility that some subject (s) may receive a dose of medication prior to being randomized.
- The protocol did not discuss the potential for an ad hoc analysis. The analysis is acknowledged in this SAP and more details will be added to an amended SAP if an analysis is performed.
- The protocol did not discuss the modified Per Protocol Analysis Set. This analysis set is described in section 6.3.6 and is used for the 24-Week analysis snapshot only.
- The SAP describes analyses for the following secondary efficacy endpoints which were not included in the protocol:
  - Time from randomization to first hemoglobin increase of  $\geq$  0.5 g/dL from Baseline.
  - Change from the baseline value for each of the following:
    - eGFR
    - serum bicarbonate
    - intact parathyroid hormone
    - C-terminal fibroblast growth factor 23
    - intact fibroblast growth factor
  - Inclusion of box and scatter plots over time of the observed value and the change from Baseline for each of the iron parameter efficacy variables, TSAT and ferritin to explore the question of their stability over time on treatment.
- The protocol specified analyses of vital signs is not included in the SAP, since no related safety concerns are anticipated.

- The protocol states that all efficacy analyses will be performed based on both the FAS and the PP/mPP analysis sets, however only the PP/mPP analyses sets will be considered. Subjects are excluded from the PP/mPP analysis sets due to confounders of efficacy and thus the FAS is not appropriate for efficacy analyses. The FAS will be used for the efficacy analysis for the 'Permitted' ESA Rescue Therapy subgroup.
- The protocol did not include the baseline by visit interaction term in the efficacy model. This interaction term is included in the SAP and will be included in the model.
- Missing endpoint observations will not be imputed using a multiple imputation (MI) linear regression approach for use in an additional sensitivity analysis as specified in the protocol sections 15.7.2 and 15.10.3.

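### Vital-sign changes stay a named safety endpoint, but the SAP drops every dedicated summary, shift table and listing, so they would be reported only through adverse events

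*SAP*

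**What the plan says.** **The endpoint.** Protocol 6.1.3 bases the safety evaluation partly on "Clinically significant changes in the subject's vital signs and laboratory test results". SAP 3.2.3 repeats it as "Clinically significant changes in laboratory test results and vital signs". SAP 9 opens its safety section with "The safety data includes adverse events, vital signs and clinical laboratory measurements".

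**The protocol's analysis.** Under Protocol 15.8.1, seated heart rate and blood pressure "will be summarized as changes from Baseline and will be classified as low, normal, or high based on reference ranges pre-specified in the SAP". The same section adds: "Vital sign abnormalities will be summarized using shift tables for all subjects and by randomized dose group". Protocol 15.1 also makes a general commitment: "All data collected will be included in by-subject data listings".

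**The SAP's analysis.** SAP 9.5 begins "No tables of descriptive statistics or by subject listings for the vital signs" and applies this to both values and changes from baseline. It then has each value classified and stored in an ADaM dataset. The classes are low/normal/high by a central laboratory reference range, plus cut-offs of diastolic < 50 or ≥ 100 mmHg, systolic < 80 or ≥ 160 mmHg, and pulse < 55 or > 110 beats/min. SAP 9.6 lists the removal of the protocol's vital-sign analyses among its changes, "since no related safety concerns are anticipated".

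**The concern.** The SAP retains the endpoint in one section and removes its planned output in another. The reason given is an expectation about the result, which is what a safety endpoint is there to check. Because 9.6 removes the protocol's vital-sign analyses as a whole, the shift tables go as well, even though 9.5 does not mention them by name.

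At stake is the completeness of the safety report from a 48-week open-label study whose stated objective includes long-term safety. A change in blood pressure or heart rate that differed between starting doses, or developed slowly in both, would have no planned table to show it unless single readings were judged clinically significant and recorded as adverse events.

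**Working it through.** No plan figure needs reproducing. The check compares what is promised with what is produced.

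| Element | Promised | Produced under the SAP |
|---|---|---|
| Named safety endpoint | Protocol 6.1.3 | Kept (SAP 3.2.3; also counted as safety data in SAP 9) |
| Collection at every visit | Protocol 13.1.2 and Table 2 | Kept (SAP 4.5) |
| Change-from-Baseline summary | Protocol 15.8.1 | Dropped (SAP 9.5, 9.6) |
| Shift tables, overall and by dose group | Protocol 15.8.1 and synopsis | Dropped (SAP 9.6) |
| By-subject listing | Protocol 15.1 and 15.8 | Dropped (SAP 9.5) |
| Low/normal/high classification | Protocol 15.8.1, with ranges set in the SAP | Derived in ADaM, tabulated nowhere (SAP 9.5) |
| Clinically significant abnormal values recorded as adverse events | Protocol 13.2.2 | Kept through the adverse event tables and listing (SAP 9.2, 9.2.1) |

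**What the last row delivers.** Protocol 13.2.2 says changes in blood pressure and pulse need not be reported as adverse events. Abnormal values must be recorded only if they are judged clinically significant, lead to stopping study drug or amount to a serious event. Those events then appear in the adverse event listing and in the treatment-emergent tables by starting dose. This gives event counts filtered by investigator judgement, in a study where the investigator knows the dose group. It does not give the number of subjects crossing the SAP's own cut-offs, the mean change from Baseline, or movement between categories by dose group.

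**Contrast within the same endpoint sentence.** The laboratory half keeps descriptive tables of values and changes, shift tables for ferritin, TSAT, hemoglobin and phosphorus, and listings (SAP 9.4).

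**Amount of data.** Protocol Table 2 records vital signs at Visit 1A and at Visits 2 to 12, so 1 + 11 = 12 scheduled visits. With 200 planned subjects:

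- all scheduled visits: 200 × 12 = 2,400 sets of blood pressure and heart rate;
- post-baseline visits (3 to 12): 200 × 10 = 2,000 sets.

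Both are ceilings before dropout and leave out re-screening, unscheduled and early termination visits.

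**Reference range.** SAP 9.5 classifies vital signs by a central laboratory range. SAP 4.5 lists the central laboratory evaluations, and vital signs are not among them. Protocol 15.8.1 calls for ranges set in the SAP. The only usable ones given are the numerical cut-offs in 9.5.

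**The case against.** A reader might infer that the endpoint cannot be reported at all, or that an unexpected blood pressure or heart rate change would appear in no output. The documents do not support either reading. The endpoint concerns clinically significant changes, and Protocol 13.2.2 sends clinically significant abnormal values into the adverse event data, which the SAP tabulates and lists in full. The flags exist in ADaM, and SAP 5.3 allows an ad hoc analysis by updating the SAP. Nor is all vital-sign output lost in the SAP's own sense of the term: 9.5 counts weight as a vital sign, and baseline weight is still tabulated under SAP 7.3.

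The sponsor also has a case for the change itself. It is declared with a reason, and SAP 2 says analysis decisions are made before database lock. Protocol 5.2 cites over 1900 exposed subjects, four studies with treatment of up to 1 year, mainly gastrointestinal adverse events, and approval for this indication. Fewer routine tables in a Phase 4 study of an approved drug is a defensible economy.

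Much of this stands. The departure is transparent, the data are kept and the worst cases would be visible. The adverse event route is still only a partial substitute, because it depends on judgement about individual readings and cannot show a moderate shift across a group. The background in Protocol 5.2 reports nothing specific on blood pressure or heart rate, and only one of the four longer studies was in non-dialysis patients. It makes a problem less likely without reporting this study's endpoint. Naming adverse events as the endpoint's only source would settle the inconsistency on paper, but would leave out the analysis that Protocol 15.8.1 specifies.

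**Conclusion.** The point holds in this form: a named safety endpoint has no dedicated output and would be reported only indirectly through adverse events, while threshold flags that could summarize it are derived and left untabulated. Disclosure in SAP 9.6 makes the departure from Protocol 15.1 and 15.8.1 visible, but the endpoint remains in SAP 3.2.3.

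In size, this is up to 2,400 scheduled sets of readings (2,000 post-baseline) that no vital-sign table or listing would show. Neither the primary hemoglobin analysis nor any efficacy result is affected. It should be corrected, but it does not threaten the trial's main conclusion.

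The conclusion assumes that the separate table shells follow the SAP text and contain no vital-sign output; they are not among the documents. It does not assume that any vital-sign effect exists.

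**What to change.** In SAP 9.5:

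1. Restore the change-from-Baseline summary for systolic pressure, diastolic pressure and pulse, by starting dose group and overall, on the Safety Analysis Set.
2. Restore a shift table for the same three measures, laid out like the laboratory shift tables in SAP 9.4 and using the cut-offs already in 9.5 to define low and high, with the values between them as the middle category. At minimum, tabulate the number and percentage of subjects with each ADaM threshold flag.
3. Replace the central laboratory reference range with those cut-offs.

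Then revise the vital-signs entry in SAP 9.6 to match. If the by-subject listing stays out, say there that this departs from Protocol 15.1.

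The cost is two or three further standard tables from data already collected and flags already derived. No new data or protocol change is needed.

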## 9.6. Summary of Changes from Protocol-Specified Analyses

- The protocol states that “All subjects who are randomized and take at least 1 dose of study medication will be included in the Safety Analysis Set.” However, the Safety Analysis Set is being defined as the set of all subjects who receive at least one dose of study medication, to allow for the highly unlikely possibility that some subject (s) may receive a dose of medication prior to being randomized.
- The protocol did not discuss the potential for an ad hoc analysis. The analysis is acknowledged in this SAP and more details will be added to an amended SAP if an analysis is performed.
- The protocol did not discuss the modified Per Protocol Analysis Set. This analysis set is described in section 6.3.6 and is used for the 24-Week analysis snapshot only.
- The SAP describes analyses for the following secondary efficacy endpoints which were not included in the protocol:
  - Time from randomization to first hemoglobin increase of  $\geq$  0.5 g/dL from Baseline.
  - Change from the baseline value for each of the following:
    - eGFR
    - serum bicarbonate
    - intact parathyroid hormone
    - C-terminal fibroblast growth factor 23
    - intact fibroblast growth factor
  - Inclusion of box and scatter plots over time of the observed value and the change from Baseline for each of the iron parameter efficacy variables, TSAT and ferritin to explore the question of their stability over time on treatment.
- The protocol specified analyses of vital signs is not included in the SAP, since no related safety concerns are anticipated.

- The protocol states that all efficacy analyses will be performed based on both the FAS and the PP/mPP analysis sets, however only the PP/mPP analyses sets will be considered. Subjects are excluded from the PP/mPP analysis sets due to confounders of efficacy and thus the FAS is not appropriate for efficacy analyses. The FAS will be used for the efficacy analysis for the 'Permitted' ESA Rescue Therapy subgroup.
- The protocol did not include the baseline by visit interaction term in the efficacy model. This interaction term is included in the SAP and will be included in the model.
- Missing endpoint observations will not be imputed using a multiple imputation (MI) linear regression approach for use in an additional sensitivity analysis as specified in the protocol sections 15.7.2 and 15.10.3.
- The protocol discusses an Interim Analysis after all subjects have completed the 24-Week Visit or Early Termination Visit. This analysis will no longer be performed. Instead, a 24-Week analysis snapshot will be performed. A selective group of data (disposition, demographic, laboratory test, and adverse events) will be cleaned and presented in a publication. The 24-Week analysis and Final analysis will be done at the end of the study.

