9.2.2. ESA Rescue Therapy

ESA use is not permitted during the study. The exception is a scenario in which all of the following conditions for ESA rescue therapy are met:

1. A subject has had 2 consecutive Hgb values of <8.0 g/dL more than 3 days apart.
2. The Investigator decides to treat the subject with ESA as per standard of care.
3. The Investigator deems it appropriate for the subject to continue in the study.
4. The subject continues in the study on study drug.

Any subject who is to receive or has received ESA therapy regardless of whether its use constitutes permitted ESA rescue therapy or not should be discussed with the Medical Monitor as soon as possible to decide whether the subject may remain in the study.

Subjects who received ESA during the study and who remain in the study will be excluded from the PP analysis set. Subgroup analyses will be conducted for these subjects.

Subjects who have had 2 consecutive Hgb values of <8.0 g/dL more than 3 days apart but do not meet the other criteria of ESA rescue therapy should complete the ET visit and discontinue from the study.

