15.7. Efficacy Analyses

All efficacy analyses will be performed based on both the FAS and the PP analysis sets. The PP analyses will be considered primary and the FAS analyses will be considered as sensitivity analyses to assess the impact of subject exclusions.

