## 5. PLANNED ANALYSES

The following analyses are planned for this trial:

- A 24-Week Analysis (to be performed after all Screening and Dose Titration Period data are available for all subjects)
- The Final Analysis (to be performed after Database lock, based on data from the entire study).

There will be two analyses; a 24-Week analysis after all subjects complete the 24-Week Dose Titration Period or have been withdrawn from the study and a Final analysis after all subjects either complete or have been withdrawn from the 48-Week study. Both analyses will be done at the end of the study.

Additionally, a “snapshot” of the data for the 24-Week analysis will be presented for publication. This publication will be based on clean data through Week 24 for key safety and efficacy measurements. This will be referred to as the “24-Week analysis snapshot”.

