### 6.3.5. Per Protocol Analysis Set

The Per Protocol (PP) Analysis Set will include all subjects in the FAS who have no major protocol deviations that affect the validity of the efficacy measurements (see section 7.2) and have not received additional treatment that affect the validity of the efficacy measurements.

The following criteria exclude a subject from the PP Analysis Set:

- Receive red blood cell transfusions within 4 weeks prior to screening or at any time during the study.
- Receive ESAs (permitted or non-permitted) within 4 weeks prior to screening or at any time during the study.
- Receive IV Iron within 4 weeks prior to screening or at any time during the study.
- Pregnancy during screening or at any time during the study.
- Overall drug compliance < 50% i.e., from randomization to the Week 48 Visit date or to Early Termination date (whichever is earlier). (See section 7.4.1 Compliance Calculation)
- Major violations of eligibility criteria as determined by review prior to database lock.

The PP analysis set will be used for the 24-Week and Final analyses.

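### The SAP drops the protocol's FAS check on exclusions and lets events after Week 24 decide who is in the Week 24 primary analysis

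*SAP*

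**What the plan says.** Protocol 15.7 asks for every efficacy analysis on both sets and ranks them: "The PP analyses will be considered primary and the FAS analyses will be considered as sensitivity analyses to assess the impact of subject exclusions".

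SAP 9.6 lists the departure. Only the PP set, or the modified PP (mPP) set for the snapshot, will be used: "Subjects are excluded from the PP/mPP analysis sets due to confounders of efficacy and thus the FAS is not appropriate for efficacy analyses". The FAS survives only for the subgroup given permitted ESA rescue. The same list drops a second sensitivity analysis: "Missing endpoint observations will not be imputed using a multiple imputation (MI) linear regression approach".

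SAP 6.3.5 then fixes PP membership. ESA, IV iron and transfusion each exclude a subject with no end date. The ESA line reads "Receive ESAs (permitted or non-permitted) within 4 weeks prior to screening or at any time during the study". The compliance line reads "Overall drug compliance < 50% i.e., from randomization to the Week 48 Visit date or to Early Termination date (whichever is earlier". The section adds: "The PP analysis set will be used for the 24-Week and Final analyses". SAP 5 says of those two analyses: "Both analyses will be done at the end of the study". SAP 6.3.6 repeats the list without the compliance line for the mPP set, which serves the snapshot only.

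The open-ended ESA exclusion comes from Protocol 9.2.2: "Subjects who received ESA during the study and who remain in the study will be excluded from the PP analysis set". Protocol 15.3.3 names non-compliance as a possible ground for exclusion but leaves the specific criteria to the SAP. The Week 48 compliance window, and its use at Week 24, are therefore SAP choices.

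**The concern.** There are two problems.

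- **The reason is circular.** The protocol wanted the FAS result because PP leaves subjects out. The SAP discards the FAS result because those subjects are left out.
- **Membership looks past the endpoint.** The primary endpoint is measured at Week 24, but whether a subject's value counts can depend on what happens in the following 24 weeks. Under Protocol 9.2.2, permitted ESA requires two consecutive hemoglobin values below 8.0 g/dL, so this exclusion selects on the outcome variable and probably moves the mean change upward. The direction for the compliance, IV iron and transfusion exclusions is not known.

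At stake is whether a reader can see how far the Week 24 estimate depends on who was removed.

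**Working it through.** **1. The plan's own precision figure.** Protocol 15.2 and SAP 4.3.1 give SD 0.9 g/dL, n = 140 and a two-sided 95% interval. Half-width = 1.96 × 0.9 / √140 = 0.149 g/dL, as stated. It serves as the yardstick below.

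**2. Does anything cut PP membership at Week 24?** SAP 5.1 limits the data analysed to visits through Week 24, but it does not limit who is in the set. SAP 8.4 does use such a cut-off for the 24-Week ESA subgroup (ESA during the Dose Titration Period), and SAP 9.3 tabulates compliance for that period split at 50%. SAP 6.3.5 uses neither. So a subject first given permitted ESA after Week 24 leaves the Week 24 PP analysis without entering the 24-Week ESA subgroup. In the end-of-study efficacy output, that Week 24 value appears only in the Final ESA subgroup, where confidence intervals are given only from 30 subjects.

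**3. Compliance window.** Let A be the tablets prescribed in Weeks 0–24, B those in Weeks 24–48, and c the compliance through Week 24. With full follow-up and no unscheduled dose changes, overall compliance is 50% when later compliance equals (0.5(A + B) − cA) / B. Each 12-week block has 84 days, so for 3-6, A = 3×84 + 6×84 = 756 and B = 6×168 = 1008.

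| Sequence (tablets/day) | A | B | c = 80%: dropped if later compliance is below | c = 40%: kept if later compliance is at least |
|---|---|---|---|---|
| 3-3 | 504 | 504 | 20% | 60% |
| 3-6 | 756 | 1008 | 27.5% | 57.5% |
| 4-4 | 672 | 672 | 20% | 60% |
| 4-6 | 840 | 1008 | 25% | 58.3% |

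Example, 3-6 at 80%: (882 − 604.8) / 1008 = 27.5%. The window works in both directions. The documents do not say how often either case would occur.

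**4. Size of the ESA exclusion.** Shift = q × (mean of retained − mean of excluded), where q is the share excluded. The documents give neither term, so both were simulated with 300,000 subjects per case and 12 cases per uptake level.

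- From the documents: two consecutive values below 8.0, the scheduled visit weeks, SD 0.9 at Week 24, and baseline within 8.5–11.5.
- Assumed: baseline mean 10.0 or 10.4 with SD 0.7; mean change rising linearly to 0.3 or 0.6 at Week 24, then flat; visit noise SD 0.4 within the 0.9; subject effect constant, ramped to Week 24, or a random walk; ESA given to all or half of those who qualify.

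| ESA uptake | Excluded | Shift in Week 24 mean (g/dL) | As share of 0.149 | Part due only to ESA after the Week 24 draw (g/dL) |
|---|---|---|---|---|
| All | 0.31–3.37% | +0.006 to +0.046 | 4–31% | 0.001–0.033 |
| Half | 0.16–1.65% | +0.003 to +0.023 | 2–15% | 0.000–0.016 |

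**5. How an FAS estimate would behave in the same cases.** With post-ESA values set to missing, it recovers the no-ESA mean to within 0.001. That follows from the set-up, because simulated rescue depends only on observed hemoglobin. With all observed values kept, and an assumed ESA rise of 1.5 or 3.0 g/dL over 12 weeks, PP minus FAS runs from −0.033 to +0.035. The two versions answer different questions.

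**6. Other exclusions.** The same formula gives only a range. An assumed 5% excluded with a 0.5 g/dL difference shifts the mean by 0.025; 10% with 0.5 shifts it by 0.05. The plan's 30% allowance is a ceiling on q because it also covers dropouts; at 30%, a difference of 0.497 would be needed to reach 0.149.

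**The case against.** **Information about excluded subjects remains.** A reader might infer that nothing is left to check the PP estimate against. The documents do not support that. SAP 9.4 summarizes laboratory change from baseline by visit for the whole Safety set, SAP 6.2 includes n, mean and SD, and SAP 6.3.3 groups by starting dose. A randomized Safety-set subject with a Week 24 change has a baseline and a post-randomization value, so is also in the FAS. That table is close to an unadjusted observed-case FAS mean, and an interval can be worked out from it. The protocol's own primary analysis (15.7.1) was an interval without imputation; the MMRM was listed as secondary. This stands and narrows the loss. What is missing is the model-based estimate that SAP 8.2 makes primary, with its interval, on the wider set.

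**The snapshot.** A reader might also infer that the mPP snapshot treats early and late enrollees unevenly, since some would already be past Week 24. That rests on estimated calendar dates, and SAP 5 describes the snapshot as using clean data through Week 24. Set against the open-ended wording in SAP 6.3.6, this is an ambiguity to clarify, not a demonstrated flaw.

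**One PP set is a reasonable choice.** It keeps the same subjects at Weeks 24 and 48, and the trial was sized on evaluable subjects at its end. Two sets give two Week 24 PP estimates, because the Week 48 MMRM also includes the Week 24 visit. This stands as a cost. It does not explain why the compliance window should decide a Week 24 result.

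**The effect may be slight.** Protocol 9.2.1 requires exit after IV iron or transfusion, so such an event before Week 24 would normally leave no later Week 24 value to lose. Very low later compliance presumes the subject stays in the trial, although non-compliance is a listed reason to discontinue. Both points are fair. Nor is the SAP's worry about confounding empty: rescue does affect an all-observed FAS mean, which is a reason to show two versions.

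**Conclusion.** The point holds on the text. The protocol's modelled check on exclusions is gone for a circular reason, and Week 24 PP membership depends on events up to Week 48. The change of sets is disclosed in SAP 9.6, PP was primary in the protocol too, and the ESA rule originates in Protocol 9.2.2.

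A reader might infer that the Week 24 result is materially biased. The documents do not show that. The ESA shift is about 0.003–0.046 g/dL, at most roughly a third of the half-width, and it rests on the assumed baseline, response and uptake. It covers only the current 8.0 g/dL trigger, not the 8.5 g/dL trigger that applied before Amendment 1. The share excluded for compliance, IV iron or transfusion is not given, so no total can be stated. Severity: minor to moderate.

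**What to change.** 1. **SAP 8.1, 8.2 and 9.6.** Add back an MMRM on the FAS for Week 24 hemoglobin change by randomized group, as a sensitivity analysis. Use all observed values, as the protocol's FAS analysis implied. Beside it, show a second version with values after the first ESA, IV iron or transfusion set to missing, labelled as a new specification because the protocol states no such rule. PP stays primary.
2. **SAP 6.3.5 and 6.3.6.** For the Week 24 analysis, apply on-study exclusions only to events through the Week 24 visit and, for PP, use compliance over the Dose Titration Period. For the mPP set, this also settles whether later rescue counts. Keep the whole-study set for Week 48. State that the primary estimate comes from the Week 24 set and that the Week 24 row of the Week 48 MMRM is supportive. Log the departure from Protocol 9.2.2 in SAP 9.6.
3. **SAP 7.1.** Add the reason for and timing of each PP exclusion to the planned counts.

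Cost: SAP wording and extra runs of a model already specified (SAP 8.2), on a set already defined (SAP 6.3.4), with a compliance period already derived (SAP 9.3). No new data are needed. The downsides are extra tables, two Week 24 PP estimates to label, and possibly a slightly smaller reported mean change.
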